7.3.4 Sound-field threshold

The purpose of this test is to establish the hearing thresholds in sound-field [0.25, 0.5, 1.0, 2.0, 3.0, 4.0, 6.0, 8.0 9.0 and 10.0 kHz] through a speaker in front position (0 degrees azimuth) according to the so-called ascending or modified Hughson-Westlake method (Figure 10). The test shall be performed with the non-test ear blocked (in case of normal or near-normal hearing or a large asymmetry with the non-test ear having significantly better hearing thresholds). The signal to be used should be warble tones.

At Visit 1 and 2, the sound-field thresholds will be measured in the aided situation with Baha 6 Max SP or Baha 5 SP depending on the randomisation order.

At visit 3 the test will be performed unaided.

7.3.5 Speech recognition in quiet

The purpose of this test is to establish the test subject's word recognition score in quiet. The speech test in quiet shall be performed using phonetically balanced words presented in sound-field through a speaker from the front (0 degrees azimuth) (figure 10). The test material shall be monosyllabic words and presented at 65 dB sound pressure level (SPL) and scores shall be recorded as % correct words. The test shall be performed with the non-test ear blocked (in case of normal or near-normal hearing or a large asymmetry with the non-test ear having significantly better hearing thresholds).

At Visit 1 and 2, the speech recognition in quiet test will be performed for the aided situation with Baha 6 Max SP or Baha 5 SP depending on the randomisation order.

At visit 3 the test will be performed unaided.

7.3.6 Sound scenarios

Subjective rating of sound, i.e. loudness, sound quality, speech understanding, own voice, artefacts and feedback after listening to sound clips in the following sound scenarios:

- Female voice in a noisy restaurant environment at 65 dB SPL
- Music at 70 dB SPL

7.3.7 Diary

Subject will complete daily the diary which covers the following items:

- Daily use of the SP (hours)
- Change of battery
- Switch to their own SP and reason for change

7.4 Safety Evaluations and Procedures

The risks and anticipated ADEs for Baha 6 Max SP or Baha 5 SP, as identified in Sections 7.2 and 8.3 of the CIP, will be assessed in the clinical investigation via reporting of all AEs/ADEs from the time of first subject first visit until last subject last visit.

Safety data adjudication may be conducted by the Sponsor's Medical Officer in accordance with the Sponsor's standard operating procedures.

7.5 Equipment Used for Evaluation of Performance and Safety

All tests shall be performed in the sound insulated room at CBAS. Equipment used for audiological testing will be calibrated in accordance with CBAS internal procedures before initiation of the investigation. No changes to the setup will be done during the investigation.

7.6 Sponsor Role in Conduct of the Clinical Investigation

The investigation will be conducted by audiologist employed by CBAS and the investigation will be conducted at CBAS facilities.

8 RISKS AND BENEFITS OF THE INVESTIGATIONAL MEDICAL DEVICE AND CLINICAL INVESTIGATION

8.1 Anticipated Clinical Benefits

There are no anticipated clinical benefits for the research subjects as they only test the investigational devices for one week in their everyday listening environment and in a laboratory setting. After study completion, the subjects will use the SP currently prescribed to him/her by a licensed audiologist within the regular healthcare system.

8.2 Anticipated Adverse Device Effects

The complete Hazard Analysis for Baha 6 Max SP can be viewed in appendix B in IB, (3).

8.3 Risks Associated with Participation in the Clinical Investigation

Baha Connect System has been thoroughly examined in terms of clinical safety and in a comprehensive analysis of available pre- and post-market clinical and non-clinical data relevant to the intended purpose of the devices in question, the clinical evaluation concludes that the Baha Connect System is safe and performs as intended, with a positive benefit-risk profile shown for the different target groups and medical indications. Although four (4) residual high risks were identified, for the Baha Connect System, none of them are associated with the sound processor.

Importantly, for this evaluation of the Baha 6 Max SP, none of the 'high' residual risks for the Baha Connect system relates to the SP (section 4.3 in IB, (3)).

The updated risk assessment for Baha 6 Max SP is presented in table 1.

Table 1. Summary of Medium/High risks for Baha 6 Max SP

Harm	Hazard Description	Severity of harm	Probability of Occurrence of Harm	Residual risk
Infection	Microbiological cross contamination for user or personnel due to poor cleaning or cut injury (various causes)	Serious	Improbable	Medium
Adverse tissue reaction	Allergic reactions of user or assembly technicians i.e. research audiologists	Serious	Improbable/remote	Medium
Life threatening injury	Device causes sparks in flammable or explosive environments leads to explosion	Catastrophic	Improbable	Medium
Permanent tissue or neural damage	Fitting the device results in too loud sound	Critical	Improbable	Medium
Permanent tissue or neural damage	Skull fracture due to impact force on the sound processor.	Critical	Improbable	Medium
Suffocation	Child swallows battery or device leading to suffocation	Catastrophic	Improbable	Medium

Suffocation	Safety line entangles around wearer's neck.	Catastrophic	Improbable	Medium
Surgical intervention and/or implantable device replacement	Device sits too tight on abutment causes loss of osseointegration	Critical	Improbable	Medium

8.4 Risk Mitigation

Control and mitigation of risks for Baha 6 Max SP are detailed in the Hazards Analysis in the IB. All risk reduction measures implemented as design controls have been verified to be effective (appendix B in IB, (3)).

Due to Covid-19 more subjects are in working age and as a possible result to that more subjects are bilateral sound processor users than anticipated. Because of this approximately 6 IMD will need to be reused during the investigation. To mitigate cross contamination between subjects the devices will be cleaned according to a validated cleaning procedure for Acoustics products (5) (6) and a Cleaning and disinfection record (7) will document which IMD that has been cleaned.

8.5 Risk-to-Benefit Rationale

The Baha 6 Max SP is the successor of the Baha 5 SP, which has been on the market for five years. Baha Connect System has been thoroughly examined in terms of clinical safety and in a comprehensive analysis of available pre- and post-market clinical and non-clinical data relevant to the intended purpose of the devices in question, the clinical evaluation concludes that the Baha Connect System is safe and performs as intended, with a positive benefit-risk profile shown for the different target groups and medical indications. Although four (4) residual high risks were identified, these were deemed acceptable given the benefits provided by the system to the patients (section 4.1 in IB, (3)).

Due to the Covid-19 pandemic, a majority of the employees at CBAS are currently working from home and a limit of 25% (N = 60) is allowed to work in the CBAS facility. Moreover, all employees at CBAS have undergone training on work safety guidelines and must comply with the following guidelines should they chose to work in the office building. In order to protect oneself and everyone else at work, the CBAS guidelines state:

- *Stay at home if you have cold and/or flu symptoms*
- *Wash your hands often and thoroughly*
- *Refrain from touching your face, nose and eyes*
- *Cover your mouth and nose with a tissue when you cough/sneeze or cough/sneeze into your elbow*

- Always keep a distance of 1.5 meters between yourself and your colleagues
- No handshaking

Do not come into the office if you have any of the following symptoms (based on the list of symptoms provided by The Public Health Agency, Folkhälsomyndigheten, Sweden):

- Cough
- Fever
- Difficulty breathing
- Runny nose/blocked nose
- Sore throat
- Headache
- Nausea
- Muscle and joint pain
- Loss of taste/smell

Everyone must be symptom-free in order to enter the facility. We ask you to reflect upon your health status each day and confirm that you are symptom-free before entering the facility in order to protect each other. When entering the facility, you need to:

1. Sign your name in the ledger to confirm that you are Covid-19 symptom free
2. Sanitize your hands at the hand sanitizer station (pump the bottle three times)
3. Walk directly to your workstation

To further decrease the risk of infection, the CBAS guidelines also state that colleagues should have a social distance when sharing cars for lunch, avoid rush hour if using public transport to/from the workplace, meeting rooms can only be used with a limited number of participants (depending on the size of the meeting room) and meeting owners are responsible for sanitizing used equipment when the meeting ends prior to leaving the room. When working in labs and/or sound booths, all equipment used must be sanitized before leaving the lab/sound booth and face masks must be used if two or more employees are in the lab at the same time. The following guidelines for the use of face masks are:

- Face masks should cover both your nose and mouth
- Do not touch the face mask while being worn to avoid contamination
- When leaving the room for a longer period throw away your face mask and use a new one when reentering
- When removing a face mask, you should use the band/ties to remove it (i.e. do not touch the material covering your mouth/nose)

Currently, visitors are not allowed into the CBAS facility. Exceptions must be approved by a member of the executive team. Hosts receiving approved visitors must ask visitors to confirm they do not have any Covid-19 symptoms. The host is also responsible for ensuring their visitors upholds the measures set out in these guidelines.

For study participants, most of the above listed guidelines will apply such as being symptom-free when asked about interest in study participation during the recruitment process and in all study visits, sanitize their hands when entering the CBAS facility, keeping a social distance of 1.5 meters to all employees in the facility, no handshaking and covering mouth/nose when coughing/sneezing. However, it should be noted that some exceptions to the above listed guidelines must apply. For example, when entering the CBAS facility, none of the study participants will have to sign their name on a ledger (in order to certify that they are symptom-free) to protect their privacy as study participants. A social distance of 1.5 meters between the clinical research audiologist and the test subject will be kept as much as possible during all visits. An exception is during implant inspection as the audiologist has to rule out infection around the implant area before the start of the study. During the implant inspection, the audiologist will use disposable plastic gloves and a face shield visor. The face shield visor will be worn by the audiologist during the whole session for each study visit. The primary reason for using a face shield visor and not face masks during study visits or in the lab is because face masks make lipreading impossible. Hard of hearing people rely highly on facial expressions and visual cues in order to compensate for missing verbal information. Thus, it is of crucial importance that we ensure all test subjects understand all information provided to them during the study, both for their own safety and the validity of the study results.

To further minimize the risk of infection for the participant and CBAS employees, the participants will either take their own car to the CBAS facility or we will book a taxi where they will be placed in the backseat (i.e. distance to the driver). Public transport to/from the CBAS facility will not be allowed. Between each visit, the audiologist will sanitize all equipment used such as technical equipment, chairs, tables, door handles, etc.

It is essential for CBAS to conduct the planned study in due time because the previous generation of Baha Sound Processor (i.e. the Baha 5 SP) was introduced in 2015 and the regulatory approved product lifetime for this device is five years. Thus, CBAS prefer to certify the investigational device and enable patients to benefit from all the technical improvements and new features introduced in the new generation of Baha, i.e. the Baha 6 Max sound processor. For more information about technical improvements and new features in Baha 6 Max, see section *1.2 The investigational medical device* in the Investigator's Brochure.

In summary, a wide range of measures to prevent Covid-19 transmission have already been applied for all employees at the CBAS facility and will be applied to all study participants to minimize the risk of infection. Face shield visors instead of face masks will be used during all visits by the audiologist as we believe that face masks will cause communication difficulties which in turn will negatively affect the safety of the participants and the validity of the study results. We believe that the benefits of performing the current study (with all preventive measures taken for both employees and study participant) outweigh the risks as this study will enable the next generation Baha sound processor to

be released to the market in due time and with that give current and future Baha users access to all the technical benefits that comes with it.

9 STATISTICAL CONSIDERATIONS

9.1 General Statistical Considerations

The investigation will have two primary analyses, one regarding Adaptive speech in noise between Baha 6 Max SP and unaided hearing ($\alpha = 0.005$) and one regarding preference between Baha 6 Max SP and Baha 5 SP ($\alpha = 0.045$). These endpoints will be evaluated using the decision rules of the Holm's test. (Ref NEJM2). With these procedures we will have a total type I error <0.05 .

For the comparison between the Baha 6 Max SP and unaided the design don't take care of period effect so the statistical analyses will be paired. For the comparison between Baha 6 Max SP and Baha 5 SP a cross over design was applied and the statistical analyses will be adjusted for period effect.

The main results for all outcome variables are the estimate of mean differences with 95% confidence interval (CI) with a descriptive p-value. The p-value will only have a confirmatory value for the two primary analyses.

For comparison between the Baha 6 Max SP and unaided Fisher's non-parametric permutation test for paired observations will be used for continuous variables and Sign test for dichotomous variables and ordered categorical variables.

For the comparison between Baha 6 Max SP and Baha 5 SP the following period adjusted analysis should be performed for continuous variables: For each subject take the difference between the measurement in second period and the measurement in first period. Then analyse these differences between the subjects randomised to Baha 6 Max SP in the first period and the subjects randomised to Baha 5 SP in the first period with Fisher's two-sided non-parametric permutation test. The Fisher's permutation test is preferable because it is non-parametric and gives consistent 95% CI.

For the comparison between Baha 6 Max SP and Baha 5 SP the following period adjusted analysis should be performed for dichotomous and ordered categorical variables: For each subject take the difference as, improved no change and worsened, between the measurement in second period and the measurement in first period. Then analyse these ordered categorical differences between the subjects randomised to Baha 6 Max SP in the first period and the subjects randomised to Baha 5 SP in the first period with Mantel-Haenszel chi-square test.

For comparison of preference of device between Baha 6 Max SP and Baha 5 SP the Sign test will be used.

The distribution of continuous variables will be given as mean, standard deviation, median, Q1, Q3, minimum and maximum and of categorical variables as numbers and percentages.

If a subject completes the cross over part but not the final visit, he will be included in the comparison between Baha 6 Max SP and Baha 5 SP but not in the comparison Baha 6 Max SP vs unaided in FAS.

The investigation will be completed when there are as many available subjects that are needed in the primary analyses.

The main analyses will be on the full analysis set (FAS) and complementary analyses on the Per protocol population. No imputation of missing data will be performed.

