7 DESIGN OF THE CLINICAL INVESTIGATION

7.1 General

[figure not shown]

Figure 4. Schematic for the investigation

This investigation is a pivotal, prospective, single-centre, randomized test order, cross-over, open label investigation comparing the performance of a new SP - Baha 6 Max SP with unaided hearing and Baha 5 SP in adult subjects with conductive or mixed hearing loss.

The evaluation of sound quality and listening effort through sound clips at visit 3 will be performed single-blinded, i.e. the test subject will not know if Baha 6 Max SP or Baha 5 SP is connected to the abutment.

The subjects include men and women aged 18 or older who are currently using the Baha Connect System (percutaneous Baha). Subjects will be screened, and 16 eligible subjects will be enrolled in the clinical investigation. Eligible subjects will be randomly assigned to one of two investigational arms using a 1:1 randomisation ratio. Subjects will be randomised either to first test the Baha 6 Max SP and thereafter Baha 5 SP or Baha 5 SP followed by Baha 6 Max SP.

After signing the informed consent, subjects will attend scheduled study visits over a three-week period to be assessed as described in the CIP Schedule of Events (Section 3). At study visits, subjects will undergo hearing assessments and safety assessments.

The first primary endpoint is to determine the hearing performance of Baha 6 Max SP in comparison with unaided hearing and the second primary endpoint is the comparison of preference between the devices. The second primary objective is to compare the hearing performance between Baha 6 Max SP and Baha 5 SP when it comes to subject preference.

Safety will be assessed by recording and summarising all AEs/ADEs and DDs. All subjects will attend an End-of-Study visit at the time they complete the investigation.

No data monitoring committee will be used for this clinical investigation.

After the investigation a subject will continue to use the SP currently prescribed to him/her.

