9.4 Sample Size Determination

First primary analysis: Baha 6 Max SP vs unaided regard Adaptive speech in noise

Assuming an individual mean difference (aided Baha 6 Max SP minus unaided) in speech recognition in noise of 16 dB SNR with a standard deviation (SD) of 12.5 (Busch et al, 2015), a total sample of 15 eligible subjects are required to provide 90% power to reject the null hypothesis for the statistical test for the primary objective (change in dB SNR) using a two sided, alpha 0.005, with Two-sided Fisher's non-parametric permutation test for paired observations. As this is an internal Cochlear investigation, patients will be recruited until the number of required patients are obtained. Hence, no dropouts are expected (8).

Second primary analysis: Baha 6 Max SP vs Baha 5 SP regarding preference of device.

Assuming that 86% prefer Baha 6 Max SP, then 16 subjects are needed for 80% power with two-sided Sign test on significance level 0.045.

In order to satisfy both sample sizes for the primary analyses 16 subjects will be randomised into the investigation.

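### The period-adjusted contrast in protocol 9.1 estimates twice the Baha 6 Max minus Baha 5 difference, and no step rescales it or fixes its sign

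*Protocol*

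**What the plan says.** Protocol 9.1 states that, for Baha 6 Max versus Baha 5, "the statistical analyses will be adjusted for period effect". For continuous variables the recipe has two steps:

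- Within each subject: "For each subject take the difference between the measurement in second period and the measurement in first period".
- Between sequences: "Then analyse these differences between the subjects randomised to Baha 6 Max SP in the first period" and those randomised to Baha 5 first, using a two-sided Fisher permutation test.

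The section gives its reason for that test: "The Fisher's permutation test is preferable because it is non-parametric and gives consistent 95% CI". It also sets the reporting standard: "The main results for all outcome variables are the estimate of mean differences with 95% confidence interval (CI) with a descriptive p-value". P-values are confirmatory for the two primary analyses only.

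The design is a two-period crossover: "Eligible subjects will be randomly assigned to one of two investigational arms using a 1:1 randomisation ratio" (protocol 7.1), and "16 subjects will be randomised into the investigation" (protocol 9.4).

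SAP 4.2.3 covers the same comparison differently. It applies a Wilcoxon signed rank test to continuous and ordered categorical variables. It mentions no sequence groups, no period adjustment, no mean difference and no CI.

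**The concern.** The within-subject difference is taken in the same time direction in both sequences. It therefore contains the device effect with a plus sign in one group and a minus sign in the other. Subtracting one group from the other removes the period effect, as intended, but adds the device effect to itself. The usual last step is to divide by 2, and 9.1 does not contain it. Nor does 9.1 say which group is subtracted from which.

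For a test this is harmless. Here, however, 9.1 makes the mean difference and its CI the main result and the p-value only descriptive for these endpoints. The quantity left without a scale or a sign is the one to be reported. These endpoints are the planned quantitative comparison with the predecessor device. A doubled difference would overstate any gain or loss, and a reversed sign would attribute it to the wrong processor.

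**Working it through.** No figure in the documents depends on this contrast, so there is none to reproduce. The check is algebra, followed by a simulation.

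**Inputs from the protocol.** D = Y(period 2) − Y(period 1) for each subject, compared between sequences (9.1). There are 16 subjects (9.4) allocated 1:1 (7.1), so about 8 per sequence.

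**Algebra.** Let δ be Baha 6 Max minus Baha 5 and π be period 2 minus period 1. Assume no carryover.

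- Baha 5 first: E[D] = π + δ
- Baha 6 Max first: E[D] = π − δ
- Baha 5-first minus Baha 6 Max-first: (π + δ) − (π − δ) = 2δ
- In the order in which 9.1 names the groups: (π − δ) − (π + δ) = −2δ

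For illustration, take δ = 2 and π = 1. The group means of D are 3 and −1. The contrast is 3 − (−1) = 4, or −4 in the order named. Half of the first is 2, the true value.

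**Interval.** With within-subject SD σ, Var(D) = 2σ². With 8 per sequence, the standard error of the raw contrast is √(2σ²/8 + 2σ²/8) = σ/√2. The raw interval is a valid interval for 2δ. Halving the estimate and both limits gives a valid interval for δ.

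**P-value.** Dividing every D by 2 rescales the test statistic identically under every permutation, so the p-value cannot change.

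**Simulation.** The settings are assumptions, because the documents give no SD for this contrast: 8 per sequence, between-subject SD 3, within-subject SD 2, 10,000 runs per row, and a t-based CI standing in for the permutation CI. Here σ/√2 = 2/√2 = 1.41.

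| True δ | Period effect | Mean raw contrast | Mean after halving | Raw CI covers δ | Halved CI covers δ |
|---|---|---|---|---|---|
| 0 | 0 | 0.00 | 0.00 | 95.0% | 95.0% |
| 1 | 0 | 1.98 | 0.99 | 90.2% | 94.9% |
| 2 | 0 | 3.97 | 1.99 | 74.4% | 94.9% |
| 3 | 0 | 6.00 | 3.00 | 48.7% | 94.7% |
| 1 | 1.5 | 1.99 | 1.00 | 90.5% | 95.2% |
| 2 | 1.5 | 3.98 | 1.99 | 74.1% | 95.1% |
| 3 | 1.5 | 5.98 | 2.99 | 50.5% | 95.1% |

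The raw contrast is about 2δ in every row, whatever the period effect. Rejection rates were identical before and after halving (for example 74.0% at δ = 2 with no period effect). In a separate run with within-subject SD 3, period effect 1 dB and a true difference of −2 dB, the raw contrast averaged −4.00 and its interval covered −2 in 85% of trials. After halving, the mean was −2.00 and coverage 94.8%. Coverage thus moves with the assumptions; the factor of 2 does not.

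**Which analyses are touched.**

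| Analysis | Method in protocol 9.1 | Affected |
|---|---|---|
| Speech in noise versus unaided (first primary) | Paired permutation test | No |
| Preference (second primary) | Sign test | No |
| Dichotomous and ordered categorical, Baha 6 Max versus Baha 5 | Mantel-Haenszel on improved, unchanged or worsened | No |
| Continuous, Baha 6 Max versus Baha 5 | Sequence contrast of D | Yes |

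The last row covers speech in noise, sound-field thresholds, speech in quiet and daily hours of use. Sound-clip ratings join it only if they are analysed as continuous.

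**The case against.** The strongest reply is that 9.1 describes a test, not a reporting formula. It never says that the raw between-sequence contrast is the number to print as the device difference, and halving is a routine step that an experienced analyst would take unprompted. A reader might infer that the report will show doubled differences; the documents do not establish that. This part of the reply stands. It does not remove the point, because 9.1 draws its CI from this same test and makes the estimate and CI the main result, while giving no other route to them.

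Second, protocol 9.11 leaves detailed analyses to the SAP. SAP 4.2.3 uses a within-subject Wilcoxon test with nothing to halve, and SAP 4.4.4 rules out additional analyses. If the SAP alone governs, no doubling occurs. This also stands, and it makes the point conditional on 9.1 being followed. But the SAP describes itself as a companion to the protocol, does not say that it withdraws the period-adjusted analysis, and offers no estimate or CI in its place. Protocol 9.1 remains the only source for the promised mean differences.

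Third, a slip would be noticeable. Protocol 9.1 calls for means and other summaries of continuous variables, and SAP 4.7 for a listing of all subject data. With 8 per sequence and complete data, the halved contrast equals the simple mean of the paired differences, so a doubled figure would be twice the gap between the device means. That makes detection likely, but it is no substitute for a definition.

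A reader might also infer that the pivotal conclusions are at risk. They are not: as protocol 9.1 sets out, the unaided comparison is paired, and for the other primary endpoint, "For comparison of preference of device between Baha 6 Max SP and Baha 5 SP the Sign test will be used".

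**Conclusion.** The point holds in a limited form. Read literally, protocol 9.1 yields an estimate and a 95% CI for twice the Baha 6 Max minus Baha 5 difference, with the sign reversed if the groups are subtracted in the order named. The factor of 2 is exact and assumes only that there is no carryover. The coverage figures illustrate assumed SDs and effects and are not properties of this trial; when the true difference is zero, coverage is not harmed.

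The reach is confined to the continuous secondary comparisons between the two processors. Both primary analyses, all p-values, the type I error and the categorical analyses are untouched. The doubling would be a matter of scale and labelling, not of test validity. It is still more than missing detail, because the unscaled quantity is what 9.1 makes the main result. It should be corrected, together with the mismatch between 9.1 and SAP 4.2.3.

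**What to change.** Add to protocol 9.1, after the continuous-variable procedure, a sentence to this effect:

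*The device effect (Baha 6 Max SP minus Baha 5 SP) is one half of the mean period difference in the Baha 5-first group minus the mean period difference in the Baha 6 Max-first group; both limits of the permutation 95% CI, taken in the same direction, are also halved.*

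An equivalent is to define each subject's value as (period 2 − period 1)/2 and keep the same stated direction of subtraction. The direction must be written in either case, since halving alone does not settle the sign.

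Then align SAP 4.2.3, so that the continuous Baha 6 Max versus Baha 5 endpoints carry this period-adjusted estimate and interval. A scaling rule copied into the SAP without the sequence contrast would have nothing to act on.

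The cost is one sentence in the protocol and a matching revision of one SAP section. It needs no new data and no change to the sample size, and the permutation p-values of 9.1 stay as they are.

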9.7 Secondary Endpoint Analyses

All the secondary endpoints in section 8.2.2 will be analysed according to the statistical methods given in section 8.1 General Statistical Considerations on both the FAS population and the Per Protocol population. The two primary efficacy analyses will also be performed on the Per Protocol population

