4.2.3 Secondary Hypotheses

For continuous variables and ordered categorical variables the Wilcoxon signed rank test will be applied and for binary variables the Binomial test will be applied when testing the null-hypothesis that the Baha 6 Max SP and the Baha 5 SP are equal.

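### For ordered categorical variables, protocol 9.1 tests only the direction of each difference and SAP 4.2.3 omits the period adjustment, so no stated analysis is both full-scale and order-adjusted

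*Protocol*

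**What the plan says.** Protocol 9.1 separates variables by type for the comparison of the two processors. Continuous variables keep each subject's numeric second-minus-first difference, which is compared between the two order groups by Fisher's permutation test. Yes/no and ordered-category variables share a second rule, which codes each subject's change in three levels: "For each subject take the difference as, improved no change and worsened, between the measurement in second period and the measurement in first period". These three-level differences are then compared with those of the subjects "randomised to Baha 5 SP in the first period with Mantel-Haenszel chi-square test".

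Protocol 9.7 sends the secondary endpoints to this rule: they "will be analysed according to the statistical methods given in section 8.1 General Statistical Considerations". The section meant is evidently 9.1. The endpoints most likely to be ordered categories are the sound-clip evaluations in protocol 7.3.6: "Subjective rating of sound, i.e. loudness, sound quality, speech understanding, own voice, artefacts and feedback after listening to sound clips". No number of response levels is given.

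SAP 4.2.3 states something different: "For continuous variables and ordered categorical variables the Wilcoxon signed rank test will be applied". It mentions neither collapsing nor a period or order adjustment, and SAP 4.4.4 plans no further analyses.

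**The concern.** For a yes/no variable, improved / no change / worsened is already the whole difference. For a rating with several levels, a one-step and a four-step advantage count the same in the test. The coding also weakens the period adjustment. A shift from first to second listening that is common to both order groups cancels when full differences are compared. When only directions are compared, it pushes subjects in both groups toward the same category and shrinks the contrast.

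The variables most likely to be affected are the sound-clip ratings, the only comparison in which the subject does not know which processor is worn. At stake is how well a trial of 16 subjects can detect a real difference on these ratings. The SAP's test avoids the coding but drops the adjustment that protocol 9.1 requires for this comparison. Reconciling the two documents by simply restoring protocol 9.1 would bring the coding back.

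**Working it through.** **Inputs.** "In order to satisfy both sample sizes for the primary analyses 16 subjects will be randomised into the investigation", and subjects are "randomly assigned to one of two investigational arms using a 1:1 randomisation ratio". That gives 16/2 = 8 expected per order. No blocking is stated, so exactly 8 and 8 is an assumption. So are two-sided alpha 0.05 for the power comparison, the number of levels, the effect, the spread and the order effect; the documents give none of these for ordered variables.

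**The plan's own figure.** The sample size reproduces.
- First primary analysis: standardised effect 16/12.5 = 1.28, two-sided alpha 0.005, paired noncentral t standing in for the permutation test. Power is 89.2% with 14 subjects and 92.4% with 15, so 15 is the smallest number reaching 90%.
- Second primary analysis: with 16 subjects the sign test rejects at 13 or more (attained alpha 0.021), and power at 86% preference is 82.4%, against 80% stated.

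No power is stated for any ordered categorical variable, so there is no further figure to reproduce.

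**The rules side by side.**

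| Rule | Keeps size of difference | Adjusts for order |
|---|---|---|
| Protocol 9.1, continuous | yes | yes |
| Protocol 9.1, ordered categorical | no | yes |
| SAP 4.2.3, ordered categorical | yes, as ranks | no |

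**Why the coding weakens the adjustment.** Let t be the device effect, p the order effect and D the second-minus-first difference. Give each rating a normal within-subject SD of 1, so that SD(D) = √2. D has mean p − t if Baha 6 Max is first and p + t if it is second.
- Full difference: contrast (p + t) − (p − t) = 2t, so p cancels. With t = 1 the standardised contrast is 2/√2 = 1.414.
- Direction only: each group's mean sign is 2Φ((p ± t)/√2) − 1.
  - With t = 1, p = 0, the means are +0.520 and −0.520. Contrast 1.041, variance 1 − 0.520² = 0.729, standardised 1.041/√0.729 = 1.219. Relative efficiency (1.219/1.414)² = 0.74.
  - With t = 1, p = 1, the means are 0.843 and 0. Contrast 0.843, average variance (0.290 + 1)/2 = 0.645, standardised 0.843/√0.645 = 1.049. Relative efficiency (1.049/1.414)² = 0.55.

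This is the limit of a very fine scale without ties. Coarser scales lose less, and a two-level scale loses nothing.

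**Power with 8 per order.** The test was the Mantel-Haenszel statistic (N − 1)r², applied by simulation to the full category difference and to its direction. Normal noise, within-subject SD 1, device effect 1.0 SD:

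| Levels | No order effect: full vs direction | Order effect 1 SD: full vs direction |
|---|---|---|
| 5 | 65.3% vs 60.7% (4.6 points) | 60.7% vs 54.1% (6.6) |
| 7 | 69.6% vs 62.2% (7.4) | 65.8% vs 54.8% (11.0) |
| 11 | 70.7% vs 60.1% (10.6) | 65.8% vs 51.5% (14.3) |

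Null rejection was 4.0% to 5.1%. With other category cut points the losses at 5, 7 and 11 levels were 5.4, 8.0 and 10.3 points without an order effect, and 8.6, 13.6 and 18.1 with 1 SD.

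A second set used within-subject correlation 0.5, device effect 0.8 SD and no order effect:
- 2 levels: no loss
- 3 levels: 67.0% vs 65.4% (1.6 points)
- 5 levels: 76.1% vs 71.6% (4.5)
- 7 levels: 80.1% vs 72.4% (7.7)
- 10 levels: 81.1% vs 71.0% (10.1)

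Over a wider grid of effects and correlations, 3 levels lost about 0 to 3 points and 4 levels about 0 to 2.5. The loss also shrinks where power is very low or near 100%: at 7 levels, correlation 0.7 and effect 1.0 SD it was 99.2% vs 98.0%.

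In the second set the SAP's signed rank test had about the power of the full difference (77.3% at 5 levels, 81.6% at 10). What it lacks is the adjustment.

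**Sensitivity to the noise.** With no order effect and raw category codes, the direction could change. Heavy-tailed noise (t, 2 df; 5 levels, effect 1.0) gave 56.9% full vs 59.0% direction. With 15% erratic raters the figures were 65.7% vs 76.9% at 5 levels and 67.6% vs 81.7% at 7. Ranking the uncollapsed differences removes most of this: over the settings examined, rank scores lost at most about 2 points to the three-level coding and gained up to about 16.

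**The case against.** Protocol 9.11 leaves the detailed analysis of every variable to the SAP, and the SAP's test does not collapse anything. If the SAP governs, the coding is never used. That stands, and it limits the point to the gap between the documents: the SAP's remedy costs the period adjustment.

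No endpoint is shown to be a multi-level ordered category. If the clip ratings are numeric or visual-analogue scores, protocol 9.1 already keeps the full difference. This stands too. The largest losses need a scale of about 11 levels, which is the kind most likely to be treated as continuous.

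The coding is also a defensible choice. It avoids treating category steps as equal, and it resists erratic ratings. That is why the fix uses ranks rather than raw codes. Ranking differences of codes still assumes that steps along the scale are comparable, but the SAP's signed rank test assumes the same.

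The clips are rated at Visit 3 in their own randomised order, not in the two home periods, and the documents do not say that this order is balanced or follows the home sequence. So the period rule does not carry over to the clips without a definition.

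A reader might infer that the lost information cannot be recovered, or that only counts of directions would be reported. The documents do not support this. Full ratings are collected, protocol 9.1 promises mean differences with 95% confidence intervals for all outcome variables, and SAP 4.7 lists all subject data. The coding acts only inside the test.

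**Conclusion.** The point holds as a conditional inefficiency and an unreconciled difference between the documents, not as an error. Protocol 9.1 adjusts for order but discards size; SAP 4.2.3 keeps size but does not adjust.

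With 8 subjects per order, the protocol's coding costs:
- nothing for dichotomous variables;
- about 0 to 3 points of power with 3 to 4 levels;
- roughly 4 to 10 points with 5 to 11 levels, normal noise, no order effect and a device effect near 1 SD, and more with a large order effect;
- nothing, or a slight gain for the coding over rank scores, with heavy-tailed or erratic ratings and little order effect.

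A reader might take a single range such as 5 to 14 points as the cost of the plan. That is not supported, because it fixes the number of levels, the effect, the order effect and the noise, and the documents give none of them. Nor do they support saying that the rule was meant only for dichotomous variables, since protocol 9.1 names both types.

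Protocol 9.1 gives confirmatory value only to the two primary p-values, and no power is planned for these ratings, so the consequence is small. The improvement is optional.

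**What to change.** In protocol 9.1 and SAP 4.2.3, keep the improved / no change / worsened rule for dichotomous variables only. For ordered categorical variables, take the uncollapsed second-minus-first difference in category, rank it across subjects, and compare the ranks between the two order groups with a Wilcoxon rank-sum test or a Mantel-Haenszel test with rank scores. For the sound clips, define first and second by the randomised clip order. Tabulate improved / no change / worsened descriptively. State the response scale of the clip ratings, so that it is clear which rule applies.

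The cost is about a sentence in each document, with no new data or subjects. The one assumption taken on, that steps along the scale are comparable, is already made by the SAP's signed rank test.
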